# **REVISION HISTORY**

*This Revision History table is provided for the benefit of study team version control. If this table will not be useful to your team, you do not need to include it.* 

Revision	Version Date	Summary of Changes	Consent
#			Change?
2	1-28-2019	Adding CEUS exams	Y
3	2-28-2019	Revising CEUS language	Y
4	5-16-2019	Adding patient calendar handouts	Ν
5	6-5-2019	Blinding clinicians from results	Y
6	1-31-2020	Adding CIBTR data collection	Y

7	4-7-2020	Adding [name] and University of	N
		Washington to study	

# 1.0 Study Summary

Study Title	Using Ultrasound Elastography to Predict Development of		
	Sinusoidal Obstruction Syndrome		
Study Design	Single-site prospective cohort study to evaluate grayscale		
	US, Doppler US, CEUS and SWE examinations in BMT		
	patients younger than 21 years.		
Primary Objective	Our central hypothesis is that SWE changes will precede		
	SOS We would like to perform a prospective cohort trial to		
	sols. We would like to perform a prospective conort trial to		
	establish optimal timing to test for SOS using SWE.		
Secondary	a) Determine if SWE can provide earlier SOS diagnosis		
Objective(s)	compared to clinical criteria and		
	b) Quantify the difference in SWE values between SOS		
	patients who would benefit from drug treatment		
	versus those who do well with supportive care		
	c) Quantify relative ability of CEUS		
	parameters versus grayscale and Doppler ultrasound.		
Research	Shear wave ultrasound elastography (SWF)		
Intervention(s)/	Shear wave annasound endstography (SWE)		
Investigational	Lumason (sulfur hexafluoride lipid-type A microspheres)		
Agent(s)	injectable suspension		
IND/IDE #			
Study Population	Children and adults, ages 1 month through 21 years who are		
Study Population	Children and adults, ages 1 month through 21 years who are undergoing allogenic or autologous myeloablative stem cell		
Study Population	Children and adults, ages 1 month through 21 years who are undergoing allogenic or autologous myeloablative stem cell transplant.		
Study Population Sample Size	Children and adults, ages 1 month through 21 years who are undergoing allogenic or autologous myeloablative stem cell transplant. 80 patients		
Study Population Sample Size Study Duration for	Children and adults, ages 1 month through 21 years who are undergoing allogenic or autologous myeloablative stem cell transplant. 80 patients Until discharge from BMT admission or to Day +100 after		
Study Population Sample Size Study Duration for Individual	Children and adults, ages 1 month through 21 years who are undergoing allogenic or autologous myeloablative stem cell transplant. 80 patients Until discharge from BMT admission or to Day +100 after BMT, whichever comes first.		
Study Population Sample Size Study Duration for Individual Participants	Children and adults, ages 1 month through 21 years who are undergoing allogenic or autologous myeloablative stem cell transplant. 80 patients Until discharge from BMT admission or to Day +100 after BMT, whichever comes first.		
Study Population Sample Size Study Duration for Individual Participants Study Specific	Children and adults, ages 1 month through 21 years who are undergoing allogenic or autologous myeloablative stem cell transplant. 80 patients Until discharge from BMT admission or to Day +100 after BMT, whichever comes first. BMT: Blood and Marrow Transplant		
Study Population Sample Size Study Duration for Individual Participants Study Specific Abbreviations/ Definitions	Children and adults, ages 1 month through 21 years who are undergoing allogenic or autologous myeloablative stem cell transplant. 80 patients Until discharge from BMT admission or to Day +100 after BMT, whichever comes first. BMT: Blood and Marrow Transplant CEUS: Contrast Enhanced Ultrasound SOS: Sinuacidal Obstruction Synchrome		
Study Population Sample Size Study Duration for Individual Participants Study Specific Abbreviations/ Definitions	Children and adults, ages 1 month through 21 years who are undergoing allogenic or autologous myeloablative stem cell transplant. 80 patients Until discharge from BMT admission or to Day +100 after BMT, whichever comes first. BMT: Blood and Marrow Transplant CEUS: Contrast Enhanced Ultrasound SOS: Sinusoidal Obstruction Syndrome SWE: Shear Wave Elastography		
Study Population Sample Size Study Duration for Individual Participants Study Specific Abbreviations/ Definitions	Children and adults, ages 1 month through 21 years who are undergoing allogenic or autologous myeloablative stem cell transplant. 80 patients Until discharge from BMT admission or to Day +100 after BMT, whichever comes first. BMT: Blood and Marrow Transplant CEUS: Contrast Enhanced Ultrasound SOS: Sinusoidal Obstruction Syndrome SWE: Shear Wave Elastography US: Ultrasound		

# 2.0 Objectives

- 2.1 Our central hypothesis is that SWE changes will precede clinical and conventional ultrasound diagnostic criteria for SOS. We would like to perform a prospective cohort trial to establish optimal timing to test for SOS using SWE
- 2.2 Determine if SWE can provide earlier SOS diagnosis compared to clinical criteria.
- 2.3 Quantify the difference in SWE values between SOS patients who would benefit from drug treatment versus those who do well with supportive care.
- 2.4 Quantify relative ability of CEUS parameters versus grayscale and Doppler ultrasound

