### 3.0 Background

3.1 Hepatic sinusoidal obstructive syndrome (SOS) is a complication of blood and marrow transplant (BMT) that is associated with high morbidity and mortality. 57,000 patients in the United States and Europe undergo BMT annually (1, 2), and SOS affects up to 15% of these patients (3). SOS pathogenesis is thought to be caused by damage to the hepatic venous endothelium due to the preparative regimen used before BMT. This damage results in obstruction of blood flow through the liver. Pathology shows collagen deposition in the sinusoids and fibrosis of venous lumens (10). The severity of the disease is correlated to the number and severity of the histological changes. Mild and moderate SOS can resolve with supportive treatment. Severe SOS (30% of SOS) is commonly associated with multi-organ failure and has a mortality rate of 80% despite available prophylaxis and treatment (Table 1) (4).

Table 1. Staging of VOD/SOS	Table 1.	Staging	of VOD/SOS 
-----------------------------	----------	---------	--------------------------

Mild : Resolved without interventions	
Moderate : Requires treatment	
• Bilirubin $> 6 \text{ mg/dl}$	
• AST > 5 times upper limit of normal	
• Weight gain $> 5\%$	
• Ascites	
Severe : Progression to Multi-organ dysfunction syndrome	

 
Respiratory failure (O2 saturation < 90 %)
 
	
Hepato renal syndrome	
• Encephalopathy	

- Severe renal failure ( creatinine > x 2)
- Bilirubin > 20 mg/ dl

SOS is most commonly defined by two clinical criteria: the modified Seattle criteria and the Baltimore criteria (Table 2) (11, 12). The modified Seattle criteria state that at least two of the following criteria must be present within 20 days of BMT: bilirubin  $\geq 2mg/dL$ ; hepatomegaly and/or ascites; and/or weight gain  $\geq 5\%$  above baseline weight (11). Pediatric SOS incidence in BMT is 20% and is higher compared to adults (13-15). Death or multi-organ dysfunction affects 30-60% children who develop SOS (16, 17). The most common definition of severe SOS is retrospective, namely death from SOS-related causes or persistent multi-organ dysfunction at 100 days post BMT. However, the European Society for Blood and Marrow Transplantation has proposed a new prospective SOS grading scheme that will likely become standard of care since it is pediatric patient specific and it is can be performed prospectively and thus can guide treatment (5).

Modified Seattle Criteria	Baltimore Criteria

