# 28.0 Resources Available

- 28.1 Describe the resources available to conduct the research: For example, as appropriate:
  - From our preliminary data, patients with no SOS or mild SOS have an average increase in velocity over baseline of 0.056 m/s at day +5 with (SD of 0.22 m/s). Our four patients with moderate and severe SOS who received defibrotide had an average increase in velocity over baseline of 0.25 m/s at day +5 (SD 0.185 m/s), we would need 245 patients (13 with moderate or severe SOS and 232 with no SOS or mild SOS) to have a power of 80% to detect a difference with alpha of 0.05. We perform approximately 40 HSCT transplants at CMH every year and in combination with the other sites, we anticipate an enrollment rate of >60% to appropriately recruit enough subjects to complete the study.
  - We anticipate needing two years to recruit enough subjects to appropriately power the study and an additional one year to analyze results.
  - CMH radiology department has three GE Logiq E10 ultrasound machines and 12 dedicated sonographers to perform the imaging requirements.
  - IDS pharmacy will supply the Lumason Contrast agent.
  - All participating sites will be required to obtain IRB approval at their local institution and CMH research coordinators will ensure all modifications, amendments, continuing reviews and AE/SAE's are electronically transferred to each site. Study SOP will be utilized for document transfers and documentation of receipt will be kept.

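### Objective 2.3 compares two groups of SOS patients that the protocol does not make identifiable, and the only power statement (28.1) is for a different contrast with mostly non-SOS comparators

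*Protocol*

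**What the plan says.** Objective 2.3 in Protocol section 2.0, which reappears in the study summary and as endpoint 4.3, is to "Quantify the difference in SWE values between SOS patients who would benefit from drug treatment versus those who do well with supportive care". Both sides of that comparison are patients with SOS.

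Three places bear on which side a moderate case would fall:
- Section 3.1, text: "Mild and moderate SOS can resolve with supportive treatment".
- Section 3.1, Table 1: "Moderate : Requires treatment".
- Section 28.1 pools moderate with severe and takes its preliminary figures from "Our four patients with moderate and severe SOS who received defibrotide".

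Section 28.1 holds the only size statement. Its comparator is patients with no SOS or mild SOS, with an "average increase in velocity over baseline of 0.056 m/s at day +5 with (SD of 0.22 m/s"). The moderate and severe patients "had an average increase in velocity over baseline of 0.25 m/s at day +5 (SD 0.185 m/s"). From these it concludes "we would need 245 patients (13 with moderate or severe SOS and 232 with no SOS or mild SOS") for 80% power at alpha 0.05. It names no objective.

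Sections 1.0, 3.3, 13.1 and 29.1 put enrolment at 80. Section 3.3 expects 12 of these to develop SOS, four of them severely. Section 6.4 says that SOS severity will be graded from clinical data and the day each grade is met recorded. It names the EBMT criteria for the date of diagnosis but no scheme for the severity grade, and it links no grade to either group of 2.3.

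**The concern.** Would-benefit is a counterfactual: it cannot be read from a patient's record. Some observable stand-in is needed, such as a severity grade, and the protocol does not choose one. With about 12 SOS patients, a few cases moved across the line change the group sizes materially. If the line is drawn after SWE values have been seen, the estimate can be shaped by the choice.

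A reader looking for the size behind 2.3 will find only 28.1. Its treatment-side group resembles one side of 2.3, but its comparator is mainly patients who never had SOS. A difference against that comparator says mostly whether SWE separates significant SOS from its absence, which is a diagnosis question. Objective 2.3 asks whether SWE separates one kind of SOS patient from another. An effect and power from the first contrast carry no assurance about the second.

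**Working it through.** **1. The figure in 28.1.** Inputs from 28.1: means 0.25 and 0.056 m/s, difference 0.25 − 0.056 = 0.194 m/s; SDs 0.185 and 0.22; groups 13 and 232. The test and its sidedness are not stated; a two-sided two-sample t-test is assumed. With SD 0.22:

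SE = 0.22 × √(1/13 + 1/232) = 0.0627; noncentrality = 0.194 / 0.0627 = 3.09; power about 87%.

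At the same allocation, 80% power needs 11 + 196 = 207 patients. The stated 245 is reached with an unstated allowance: a rank-sum test at its minimum relative efficiency of 0.864 gives exactly 13 + 232, and a 15% loss gives 207 / 0.85 ≈ 244. So 245 is undocumented rather than shown to be wrong.

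**2. Who is in the 28.1 comparator.** Section 3.1 gives SOS incidence of up to 15% overall and 20% in children.
- At 15%: 245 × 0.15 ≈ 37 SOS; less 13 leaves about 24 mild; (232 − 24) / 232 ≈ 90% without SOS.
- At 20%: 245 × 0.20 = 49 SOS; less 13 leaves 36 mild; (232 − 36) / 232 ≈ 84% without SOS.

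**3. The 28.1 contrast with 80 patients.** The 28.1 share, 13/245 = 5.3%, gives about 4 moderate or severe cases in 80. Power for 4 v 76 with SD 0.22 is about 40%. It reaches about 79% only if all 12 expected SOS cases were moderate or severe (12 v 68). The 80% figure therefore does not describe the planned enrolment even for its own contrast.

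**4. The 2.3 contrast with 12 SOS patients.** The documents give no SD within SOS. Assume, for illustration only, that the 28.1 SDs and difference carry over.

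Pooled SD: s² = [(n₁ − 1) × 0.185² + (n₂ − 1) × 0.22²] / 10. Half-width = t(0.975; 10 df) × s × √(1/n₁ + 1/n₂), with t = 2.228. Power is from the noncentral t with noncentrality 0.194 / SE.

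For 4 v 8: s² = (3 × 0.034225 + 7 × 0.0484) / 10 = 0.04415, s = 0.210; SE = 0.210 × √(1/4 + 1/8) = 0.129; half-width = 2.228 × 0.129 = 0.287.

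| Treatment side v supportive side | Half-width, pooled SD | Power | Half-width, SD 0.22 in both | Power |
|---|---|---|---|---|
| 4 v 8 | 0.287 | 27.6% | 0.300 | 25.6% |
| 6 v 6 | 0.261 | 32.2% | 0.283 | 28.2% |
| 10 v 2 | 0.326 | 22.5% | 0.380 | 17.8% |

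The 4 v 8 split is severe cases against the rest, using section 3.3. The 10 v 2 split is an illustrative extreme: it scales up 4 of 5, on the unstated premise that the four treated patients in 28.1 are among the five SOS patients in 3.3. In every row the half-width exceeds 0.194 m/s.

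**The case against.** The strongest reply is that 2.3 is a secondary objective already worded as quantification, so it needs no power statement; that 28.1 never claims to size it; and that operational group definitions are commonly left to the analysis plan, which is not at hand. The first two points stand. Low power is not in itself a fault of 2.3, and the protocol does not assert that 245 patients or 80% power support it. The third stands in part. An analysis plan could define the groups, but it would leave the unclear pointers in the protocol, and 28.1 would still be the only size statement printed beside an enrolment of 80.

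A reader might infer that the protocol defines the two groups in contradictory ways. The text does not go that far. The sentence in 3.1 and Table 1 are background, neither refers to 2.3, and they can be read together: saying that moderate SOS can resolve is weaker than a definition, and treatment in Table 1 could include supportive treatment. The accurate statement is that the groups are not identifiable and the pointers are unclear.

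A reader might also infer that patients will be grouped by receipt of defibrotide. Section 28.1 uses receipt only to describe four preliminary patients; the groups it sizes are set by grade.

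Finally, one might take the move from 4 v 8 to 10 v 2 as proof that the placing of moderate cases decides the result. It is not proof. The 10 v 2 split rests on 4 of 5 patients, the 13/245 share would give about 4 v 8 even with moderate cases on the treatment side, and precision is similar across the splits.

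**Conclusion.** The point holds in this form: the two SOS groups of 2.3 and 4.3 cannot be identified from the protocol, and the effect and power in 28.1 belong to another contrast and to 245 patients rather than 80. This mismatch rests on the wording of 2.3 and 28.1 alone and does not depend on how section 3.1 is read.

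The size is conditional. With 12 SOS patients and the 28.1 SDs carried over, the 95% half-width is about 0.26–0.33 m/s, or up to 0.38 with SD 0.22 in both groups. Power for 0.194 m/s is roughly 18–32%. A true within-SOS SD or difference unlike those in 28.1 would change these figures. They show that 2.3 can be only a rough estimate; they do not show that it should be dropped or that more patients are required. No view is taken on which patients should be treated.

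**What to change.** - In 2.3 and 4.3, restrict both groups to SOS patients and define them by the severity grade that section 6.4 records with its date. Name the grading scheme, since 6.4 names EBMT only for diagnosis, and name the cut. Fix both before SWE values are examined, and state that receipt of defibrotide does not assign the group. Because 6.4 has clinical variables extracted from the records retrospectively, say that grading is done without sight of the SWE values.
- Reconcile the text of 3.1, Table 1 and 28.1 on how moderate SOS is described.
- In 28.1, state that the 80% power belongs to 245 patients and to moderate or severe SOS v no or mild SOS, and that it does not support 2.3.
- Describe 2.3 as estimation, reporting the difference with its 95% interval, and give the expected precision above with its assumption.

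The cost is wording in 2.3, 4.3, 3.1, 6.4 and 28.1, with no added patients or examinations. The downside is that 2.3 becomes explicitly estimation-only and the stated power looks less favourable.

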### 3.0 Background

3.1 Hepatic sinusoidal obstructive syndrome (SOS) is a complication of blood and marrow transplant (BMT) that is associated with high morbidity and mortality. 57,000 patients in the United States and Europe undergo BMT annually (1, 2), and SOS affects up to 15% of these patients (3). SOS pathogenesis is thought to be caused by damage to the hepatic venous endothelium due to the preparative regimen used before BMT. This damage results in obstruction of blood flow through the liver. Pathology shows collagen deposition in the sinusoids and fibrosis of venous lumens (10). The severity of the disease is correlated to the number and severity of the histological changes. Mild and moderate SOS can resolve with supportive treatment. Severe SOS (30% of SOS) is commonly associated with multi-organ failure and has a mortality rate of 80% despite available prophylaxis and treatment (Table 1) (4).

Table 1. Staging of VOD/SOS	Table 1.	Staging	of VOD/SOS 
-----------------------------	----------	---------	--------------------------

Mild : Resolved without interventions	
Moderate : Requires treatment	
• Bilirubin $> 6 \text{ mg/dl}$	
• AST > 5 times upper limit of normal	
• Weight gain $> 5\%$	
• Ascites	
Severe : Progression to Multi-organ dysfunction syndrome	

 
Respiratory failure (O2 saturation < 90 %)
 
	
Hepato renal syndrome	
• Encephalopathy	

- Severe renal failure ( creatinine > x 2)
- Bilirubin > 20 mg/ dl

SOS is most commonly defined by two clinical criteria: the modified Seattle criteria and the Baltimore criteria (Table 2) (11, 12). The modified Seattle criteria state that at least two of the following criteria must be present within 20 days of BMT: bilirubin  $\geq 2mg/dL$ ; hepatomegaly and/or ascites; and/or weight gain  $\geq 5\%$  above baseline weight (11). Pediatric SOS incidence in BMT is 20% and is higher compared to adults (13-15). Death or multi-organ dysfunction affects 30-60% children who develop SOS (16, 17). The most common definition of severe SOS is retrospective, namely death from SOS-related causes or persistent multi-organ dysfunction at 100 days post BMT. However, the European Society for Blood and Marrow Transplantation has proposed a new prospective SOS grading scheme that will likely become standard of care since it is pediatric patient specific and it is can be performed prospectively and thus can guide treatment (5).

Modified Seattle Criteria	Baltimore Criteria
Two of the following criteria must be present with in 20 days of SCT	Bilirubin must be $\geq 2mg/dL$ before 21 days SCT and two of the following criteria must be present
Bilirubin $\geq 2mg/dL$	Ascites (Physical exam or radiographic)
Hepatomegaly increased over baseline	Weight gain $\geq$ 5 %above baseline weight *
Ascites (Physical exam or radiographic) and /or Weight gain $\geq$ 5 %above baseline weight	Hepatomegaly increased over baseline

#### Table 2. A table to show the clinical criteria for veno-occlusive disease

3.2 Recently, a promising drug for SOS treatment has been discovered, defibrotide, which is a DNA derivative from porcine intestine that protects and repairs endothelial cells. Prior trials showed that defibrotide decreased the incidence of multi-organ failure and death from SOS. The main caveat is that treatment must be initiated very close to the time of clinical diagnosis using the Baltimore criteria to be effective (7). A study showed that 31/33 (94%) patients had complete remission of their SOS when treated with defibrotide <3 days after diagnosis, whereas only 3/12 (25%) patients had complete remission when treated >3 days of diagnosis (7). However, universal

prophylaxis is infeasible due to high drug costs (\$155,000 for patient) (8). There is a critical need for an early and effective SOS diagnostic test that can identify patients who would benefit from defibrotide treatment.

Several adult and pediatric prospective studies have evaluated the efficacy of grayscale and Doppler ultrasound (US) in diagnosing SOS (18-20) and have concluded that the clinical criteria are superior to US criteria for SOS diagnosis. The main reason for this conclusion is that conventional US is able to diagnose SOS only after the clinical diagnosis (18-20). This research has resulted in multiple recent guidelines recommending US only for confirming clinical diagnoses or following disease progression and not for primary diagnosis (5, 6). Ultrasound shear wave elastography (SWE) has been shown to effectively diagnose passive hepatic congestion. Fontan physiology is the best studied example. SWE values markedly increased after the Fontan operation. This surgery connects the hepatic venous circulation to the pulmonary arteries exposing the liver to increased resistance from the pulmonary circulation thereby increasing hepatic venous congestion (21). Additionally, the effect sizes in the Fontan studies are large compared with the effect sizes in hepatic fibrosis studies (21, 22). The common thread of hepatic venous congestion between Fontan physiology and SOS physiology led us to hypothesize that SWE could be useful in SOS diagnosis. Additionally, preliminary SWE studies in adults showed that it might be useful in the setting of SOS (23). In addition to SWE, the use of contrast-enhanced ultrasound (CEUS) for evaluation of variability of blood flow in patients with SOS versus those without has also become of interest.

CEUS uses an intravenous injection of microbubble contrast agents and is an established method to detect and characterize focal liver lesions; it also has been used to diagnose liver vein thrombosis. [Wilson, Abdom Radiol (NY), 2018; Dietrich, Ultrasound Int Open, 2018; Trenker, BMT, 2018] The value of CEUS in VOD/SOS is evolving; however, the findings from two case reports suggest that the performance of CEUS could help to facilitate an early diagnosis and clinical follow-up of VOD/SOS. [Fontanilla, J Ultrasound Med, 2011; Trenker, BMT, 2018] For example, in a case report of a patient who developed signs and symptoms of VOD/SOS 44 days after HSCT, CEUS showed heterogeneous uptake of contrast in VOD/SOS, and the areas of delayed enhancement corresponded to stiff areas on SWE; the contrast-enhanced sonographic pattern normalized after specific treatment. [Fontanilla, J Ultrasound Med, 2011] In another case report—this one in a patient with a clinical diagnosis of VOD/SOS after HSCT-CEUS showed a normal arterial and portal venous contrast medium inflow, but almost no portal venous and parenchymal hepatic enhancement. [Trenker,

BMT, 2018] The CEUS findings were novel, representing VOD/SOS pathophysiology and hepatic microvascularization dysfunction for the first time. [Trenker, BMT, 2018] Since SOS is a heterogeneous disease, we believe that contrast enhanced ultrasound may be useful in characterizing areas that are more severely involved in SOS and areas that are less severely involved. By interrogating both areas using contrast kinetics and SWE and correlating the values to disease severity, we hope to gain more insight into which areas (severely involved or less severely involved) are most responsible for the clinical sequelae and outcomes in SOS.

3.3 The long-term goal of our research is to accurately identify SOS patients who would benefit from defibrotide treatment using US SWE. The overall objective of this study is to validate SWE as an early diagnostic marker for SOS. Our central hypothesis is that SWE changes will precede clinical and conventional US diagnostic criteria for SOS. Our hypothesis has been formulated on the basis of our own preliminary data. We completed the first prospective cohort trial demonstrating that US SWE provides SOS diagnosis (80% sensitivity and 67% specificity) nine days earlier than current clinical criteria (9). SWE is widely available, has no known side effects, and is easy to learn and interpret. Our study enrolled 25 high-risk BMT patients over 18 months (five with SOS and two with severe SOS). More data is needed to determine the optimal window for testing to balance between improved test characteristics and early detection of disease. We propose conducting a prospective cohort study with 80 additional patients, 12 of which will likely develop SOS (including four with severe SOS) to optimize SWE timing. This study will increase the confidence in the findings from our preliminary study and allow us to test SWE against newly published clinical criteria. The rationale for the proposed research is that, if SWE can diagnose SOS earlier than clinical criteria, then SWE can guide early initiation of SOS treatment.

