# 4.0 Study Endpoints

- 4.1 To perform a prospective cohort trial to establish optimal timing to test for SOS using SWE.
- 4.2 Determine if SWE can provide earlier SOS diagnosis compared to clinical criteria.
- 4.3 Quantify the difference in SWE values between SOS patient who would benefit from drug treatment versus those who do well with supportive care.
- 4.4 Quantify relative ability to CEUS parameters versus grayscale and Doppler ultrasound.

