### Ultrasound Examinations and Timeline

After enrollment and within two weeks prior to starting their conditioning regimen, a limited abdominal US with Doppler measurements of the hepatic arteries, hepatic and portal veins, contrast enhanced ultrasound (CEUS) of the liver, as well as SWE will be performed.

Subjects will be undergo US examinations based on disease course as outlined below:

- 1. All Patients: Patients will undergo limited abdominal US with Doppler, CEUS and SWE once a week upon admission for conditioning until the patient day +30 BMT or discharge, whichever comes first.
- 2. Inpatient SOS: patients will undergo limited abdominal US with Doppler, CEUS and SWE once a week upon admission for conditioning until resolution of SOS.
- 3. Late Onset SOS: patients will undergo limited abdominal US with Doppler, CEUS and SWE once a week upon admission for conditioning until resolution of SOS.

The clinical team will order US, CEUS and SWE exams when patients have clinical suspicion for SOS and we will include these exams in our analysis. All imaging will be performed using GE Logiq E9 US machines by dedicated pediatric sonographers and interpreted by board-certified pediatric radiologists. Twelve shear wave velocity measurements will be taken 2-3 cm below the liver capsule at the mid-clavicular line in the right hepatic lobe and another 12 will be taken in the left hepatic lobe near midline

avoiding areas of vasculature (24). By necessity, the sonographer and interpreting radiologist will not be blinded to the clinical status of the patient. US and clinical data will be collected weekly and managed using REDCap electronic data capture tools hosted at Children's Mercy Hospital (25).

	ALL PATIENTS		INPATIENT SOS	LATE ONSET SOS
	Prior to	Start of Conditioning	Through	Through Resolution of
	Conditioning	through Day +30	Resolution of SOS	SOS
	Screening	Once per Week	Once per Week	Once per Week
Limited Abdomen and Limited Abdominal Doppler Ultrasound	X	Х	Х	X
Contrast Enhanced Ultrasound	X	X	X	X
Ultrasound Elastography	X	X	X	X

Table 3. Ultrasound Timeline

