# 29.0 Multi-Site Research

*29.1* Study-Wide Number of Subjects: 80

29.2 Study-Wide Recruitment Methods: CMH will be the only site recruiting subjects. The University of Washington – Seattle's involvement is to provide imaging consulting. [name] will have access to our PACS system for evaluation of the imaging for analysis and image protocol validation.

- All required approvals (initial, continuing review and modifications) will be submitted to CMH IRB (IRB of record) for approval and letter of correspondence provided by CMH IRB will be sent to each site for local IRB (relying IRB) approval. Each site will be required to send documentation of local IRB approval.
- All modifications will be communicated to sites and approved (including approval by the site's IRB of record) before the modification is implemented.
- All engaged participating sites will safeguard data, including secure transmission of data, as required by local information security policies.
- All local site investigators conduct the study in accordance with applicable federal regulations and local laws.
- All non-compliance with the study protocol or applicable requirements and any unanticipated problems will be reported in accordance with local policy.
- *29.3* Describe the method for communicating to engaged participating sites:
  - All education and training to researchers and research staff will be provided by CMH and documentation of training will be recorded.
  - All reportable events must be communicated within 5 business days of notification of reportable event to CMH study staff for submission to CMH IRB (IRB of record).
  - Interim results will be communicated through virtual meetings and electronic communication as they become available.
  - The closure of a study will be communicated through electronic documentation of correspondence letter from IRB of record to participating sites for relying IRB documentation.
  - •

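### Section 3.3 calls the study a validation of SWE, but the testing window is to be chosen in the same 80 patients (about 12 SOS cases); accuracy at that window is a development result and tends to be too high unless corrected.

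*Protocol*

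**What the plan says.** Section 3.3 gives two purposes for one data set. The first is validation: "The overall objective of this study is to validate SWE as an early diagnostic marker for SOS". The second is selection. The 80 additional patients are recruited with "12 of which will likely develop SOS (including four with severe SOS) to optimize SWE timing", because "More data is needed to determine the optimal window for testing to balance between improved test characteristics and early detection of disease". Test accuracy is thus one of the stated criteria for choosing the window.

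Section 1.0, objective 2.1 and endpoint 4.1 make selection the primary aim; 4.1 reads "To perform a prospective cohort trial to establish optimal timing to test for SOS using SWE". None of the listed objectives or endpoints speaks of validation.

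There is one cohort: section 29.1 has "Study-Wide Number of Subjects: 80", with one recruiting site. The candidate times come from the scan schedule in section 6.1: "once a week upon admission for conditioning until the patient day +30 BMT or discharge, whichever comes first".

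Section 3.3 also reports a separate preliminary cohort of 25 high-risk patients, five with SOS, with 80% sensitivity and 67% specificity. The protocol states no cut-off or time from that cohort to be tested in the new patients. Section 28.1 names day +5, but for a difference in mean velocity change and not as a diagnostic rule.

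**The concern.** Validation means testing a rule settled beforehand. If several weekly times are compared and the one with the best sensitivity and specificity is kept, its observed accuracy includes the chance variation that helped it win. With about 12 cases, each case is worth about 8 points of sensitivity (1/12 = 8.3%), so that variation is large.

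Section 3.3 hopes that SWE can guide early initiation of SOS treatment. A sensitivity that is partly selection effect, yet labelled as validated, would be a weak basis for that use.

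**Working it through.** **1. The protocol's case count.** Section 3.1 says that "SOS affects up to 15% of these patients": 80 × 0.15 = 12, as stated. With 30% severe, 12 × 0.30 = 3.6, or about 4, as stated. The 20% paediatric incidence in 3.1 would give 80 × 0.20 = 16. The check uses 12 cases and 68 non-cases.

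**2. Inputs from section 28.1.** Mean rise in velocity over baseline at day +5 is 0.056 m/s (SD 0.22) with no or mild SOS and 0.25 m/s (SD 0.185) with moderate or severe SOS. The difference is 0.25 − 0.056 = 0.194 m/s, and 0.194/0.22 = 0.88 SD. The documents give no such figures for all SOS against none, or for other weeks, so their use here is an assumption.

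**3. Further assumptions.** Normal data; 4 to 6 weekly times; within-patient correlation 0.3 to 0.8; the time chosen is the one with the largest sensitivity + specificity.

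**4. Fixed cut-off.** Set the cut at a true specificity of 67%, the preliminary figure. It lies 0.440 × 0.22 = 0.097 m/s above the non-case mean. True sensitivity at a shift of 0.194 is Φ((0.194 − 0.097)/0.185) = Φ(0.525) = 70%.

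**5. Simulation.** In each simulated study, choose the best time, then subtract the true sensitivity of the chosen rule from its apparent sensitivity. Each setting had 2,000 to 6,000 runs. Where the cut-off is also chosen, it is the value maximising sensitivity + specificity, with case SD 0.185 or 0.22.

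| True accuracy over the weeks | Inflation, time chosen only | Inflation, time and cut-off chosen |
|---|---|---|
| Equal at 4 to 6 times | 8 to 13 points | 19 to 24 points |
| A peak among five times (shifts 0.05, 0.12, 0.194, 0.25, 0.20; true sensitivity 40, 55, 70, 80, 71%) | 6 to 9 | 16 to 20 |
| One time clearly best (shifts 0, 0.05, 0.10, 0.194, 0.35; true sensitivity 30, 40, 51, 70, 91%) | 1 to 3 | 11 to 13 |
| One time fixed in advance | about 0 | 13 to 14 (cut-off only) |

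Example: five equally accurate times, correlation 0.5. Choosing the time alone gives apparent sensitivity 81% against a true 70%. Choosing time and cut-off, with SD 0.22 in both groups, gives 83% against 61%.

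**6. Precision, a separate matter from bias.** Even for a rule fixed in advance, 10 of 12 cases detected (83%) has an exact 95% interval of 52% to 98%, and 46 of 68 non-cases correctly negative (68%) has 55% to 78%.

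**The case against.** The strongest reply is that this is one word in a background section. The numbered objectives and endpoints do not say *validate*, and none names sensitivity or specificity. Cut-off rules, cross-validation and optimism correction commonly sit in a statistical analysis plan, which is not shown. This stands in part. The silence on correction is not a fault of the protocol, and a reader who infers that the reported accuracy is certain to be too high goes further than the text allows. It does not remove the conflict, because section 3.3 itself states the overall objective and says that the window will be chosen partly on test characteristics.

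A second reply is that the two aims can coexist, and this also stands. The 80 are new patients, meant among other things to increase confidence in the preliminary findings. A preliminary rule fixed beforehand could be tested in them without selection bias. It would be wrong to infer that the aims are incompatible; the bias attaches only to what is newly chosen.

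A third reply concerns size. The protocol speaks of optimising timing and nowhere says that a cut-off will be re-chosen. A gap such as 83% against 61% is therefore not what the text implies, and more than half of it comes from the cut-off (about 13 of 22 points arise at a single fixed time). Equal accuracy at every week is also the least favourable assumption. The timing-only range of 1 to 13 points is the one that matches the protocol.

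**Conclusion.** The conflict is real and lies in the protocol's own wording: a study that selects its testing window partly on accuracy cannot also validate that window in the same patients. Left uncorrected, sensitivity at the chosen window is inflated by about 1 to 13 points when only the time is chosen. If a cut-off is re-chosen too, it is inflated by about 15 to 22 points in most settings, and by 11 to 24 across all those tried. The direction was upward in every setting that involved a choice.

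The sizes rest on normal data, the assumed number of scans and correlation, and an effect taken from moderate or severe against no or mild SOS at day +5. They show the order of magnitude and do not forecast the result. Nothing here shows that the lead time over clinical diagnosis would be exaggerated; that was not examined.

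**What to change.** In sections 3.3 and 4.0, describe the choice of window, and of any new cut-off, as development. State that its accuracy will be reported after bootstrap or cross-validated optimism correction that repeats the whole selection in each resample.

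Keep *validate* for one rule, a cut-off and a time, fixed from the preliminary 25-patient cohort before the new data are analysed. Apply it unchanged to the new patients, with exact intervals for sensitivity and specificity. The protocol does not give the preliminary cut-off, so it must be taken from that study's records and written in. Note two limits: the earlier cohort was high-risk, and section 6.4 now dates diagnosis by EBMT criteria, so the comparison is not like for like. If no such rule can be fixed, drop *validate* from 3.3.

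No extra patients or scans are needed. The cost is wording, a little more analysis and less favourable headline accuracy.
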